# **Study Summary**

Title	Heart Failure Optimization Study
Short Title	HF Opt Study
ZOLL Protocol Number	90D0109
Study Design	Prospective observational study
Study Duration	Approximately 60 months
Study Center(s)	Multi-center, Thirty to eighty sites, in US and Europe
Primary Objective(s)	Observe the rate of recovery of ventricular function (EF>35%) between 90 and 180 days in newly diagnosed HF with reduced EF patients.
Study Population	Patients who were prescribed the wearable cardioverter defibrillator (WCD) $\leq$ 10 days post-discharge after hospitalization for a primary reason of new onset HF ( $\leq$ 30 days since first HF hospitalization), with ischemic or nonischemic cardiomyopathy, and have already used a WCD for 90 $\pm$ 14 days. For the first 90 days of WCD use, patients will be enrolled in a pre-study registry.
Intervention	An FDA-approved, CE marked WCD will be prescribed for up to 6 months of use after hospital discharge, with the option for longer use under physician discretion
Study Size	Up to 600 for the study, up to 1400 for the pre-study registry
Reference therapy	NA

## 1 Introduction

This document is a protocol for a human research study. This study is to be conducted according to US and international standards of Good Clinical Practice (International Conference on Harmonization ICHE6), the Code of Federal Regulations Title 21 parts 803 and 812, and other applicable government regulations and Institutional research policies and procedures.

## 1.1 Background

#### 1.1.1 Sudden Cardiac Death in Heart Failure

Sudden cardiac death (SCD) is usually defined as death from a cardiac etiology within an hour of the onset of symptoms in a person who otherwise appeared in a stable clinical state. These deaths are often attributed to a cardiac arrhythmia, of which ventricular fibrillation is the most common. In the United States, SCD is the leading cause of death accounting for nearly 350,000 deaths per year or approximately 1,000 deaths per day. Although a preexisting heart condition may not be present, patients known to have heart failure (HF) have been shown to have a higher risk of SCD. Among patients with HF, those with ventricular dysfunction as evidenced by a lower left ventricular ejection fraction (LVEF) have a particularly high risk of SCD.

Over one million hospital admissions for acutely decompensated heart failure occur annually in the USA and one in nine death certificates list heart failure as a related cause. Within the Veterans Affairs Health Care System, mortality after discharge has declined but remains significant (over 10% at 90 days post-discharge in 2006), and re-admission rates have trended higher (over 6% at 30 days in 2006). Similar data has been reported among Medicare recipients. Sudden cardiac death may account for half of the cardiovascular mortality experienced.

Another method of SCA risk protection frequently used after HF hospitalization is the wearable defibrillator (WCD). WCDs have been commercially approved for use by the FDA and CE marked for Europe since 2001. Since a WCD is non-invasive and can easily be removed, it makes an ideal device for protecting HF patients when SCD risk is high yet recovery is still possible. After medications have been titrated into appropriate doses and the EF has been given time to recover, the WCD can be removed and an assessment for ICD implantation due to permanent SCD risk can be performed.

#### 1.2 Preclinical Data

NA

#### 1.3 Clinical Data to Date

Previous clinical data reveals that the following questions remain controversial subjects in newly diagnosed HF patients:

- 1) How long does it take to achieve optimal medical therapy?, and therefore,
- 2) When to implant an ICD in a newly diagnosed patient?, and
- 3) How often and when to measure EF recovery?

Titration to therapeutic levels is generally not achieved within three months of initiation  for some drugs known to improve ventricular dysfunction, and improvements in heart failure symptoms and ventricular dysfunction may occur after optimization of medical therapy over time.

A recent retrospective study of Medicare patients linked to the National Cardiovascular Data ICD Registry showed a very low rate of guideline-directed medical therapy being achieved in the 90 days before ICD implantation . Only 61.1% had filled their prescriptions for a HF beta-blocker plus an angiotensin-converting enzyme inhibitor or angiotensin receptor blocker at least once during the 90 days before ICD implantation, and only 28.3% had a supply for ≥80% of the 90 days. Interestingly, those with the shortest duration of HF and most recent evaluation of EF were the least likely to receive guideline-directed medical therapy. Death within one year occurred more frequently in those patients not receiving any guideline-directed medical therapy even after adjusting for patient characteristics, HF severity, and comorbidities.

Although EF is typically measured in the beginning, and usually at some follow-up period, it is unknown how often EF should be measured and what "recovery" of LV dysfunction means in terms of outcomes. The IMAC-2 study looked at myocardial recovery in newly diagnosed NICM

<sup>10 Feldman et al., "Use of a Wearable Defibrillator in Terminating Tachyarrhythmias in Patients at High Risk for Sudden Death: Results of WEARIT/BIROAD," PACE 2003; 27:4-9.

<sup>11 Fonarow et al., "Dosing of Beta-Blocker Therapy Before, During, and After Hospitalization for Heart Failure," Am J Cardiol 2008; 102:1524–1529.

<sup>12 Gustafsson et al., "Treatment with beta-blockers in nurse-led heart failure clinics: Titration efficacy and predictors of failure," Euro J of Heart Failure 2007; 9:910–916.

<sup>13 Roth et al, "Use of Guideline-Directed Medications for Heart Failure Before Cardioverter-Defibrillator Implantation," JACC 2016; 67:1062-9.

patients with EF  $\leq$ 40%. They found that 40% of patients had an EF $\geq$ 45% at 6 months, and 25% had an EF $\geq$ 50% . Among DEFINITE trial subjects with follow-up EF measurements, 32% improved EF over 35% during the first two years of the trial despite enrollment criteria of EF  $\leq$ 35% and "stable" HF for at least 30 days . They also found that patients with LVEF improvement had a decreased risk of total mortality, although no reduction in arrhythmic events. In contrast to the IMAC-2 study, the DEFINITE study excluded reversible cardiomyopathies, which may explain the lower recovery rate seen in DEFINITE patients.

### 1.4 Study Device

#### 1.4.1 Wearable Cardioverter Defibrillator (WCD)

To date, several studies have demonstrated the impact WCD's have had in successfully resuscitating patients from ventricular tachyarrhythmias. In fact, the first shock termination success of 98% for sustained ventricular tachyarrhythmias and the 94% survival to conscious emergency room arrival is far superior to any other form of outpatient resuscitation. The highest rates of survival from SCA secondary to ventricular tachyarrhythmias (53%) are reported to be in casinos owing to the rapid defibrillation afforded by witnessing most patient collapses (surveillance is constant) and close availability of defibrillators. Since no witness is required for a WCD to detect and defibrillate, when a WCD is worn it provides outpatient defibrillation faster than that afforded from constant, close human observation.

Wearable defibrillators have shown great success in treating SCA. However, the data confirming the overall impact of WCD by allowing for LVEF recovery is limited. As the device is being used routinely in some centers for selected high-risk HF patients after discharge, a prospective study is warranted to confirm that the WCD benefits these patients, both in terms of SCD protection and by allowing for ICD deferment until LV recovery may occur.

## 2 Study Objectives

## 2.1 Primary Objective(s)

The primary objective of this study is to observe the rate of recovery of ventricular function (EF>35%) between 90 and 180 days in newly diagnosed HF with reduced EF patients who were prescribed the WCD while being initiated on their HF medications. This will be measured from EF closest to before hospital discharge, then at 90, 180 and 360-days after WCD start, regardless of continued WCD use, prior EF improvement, or ICD implantation. While approximately one-third of the patients will likely experience EF recovery in the first 90 days, we hypothesize that an additional 5-10% of patients will experience EF improvement between 90 and 180 days as GDMT is achieved. This would be considered clinically significant in terms of the potentially avoided ICD implantations. Outcomes will be tracked and reported for three pre-specified groups based on assessment of SCD risk at 90 days of WCD use:

- 1) Patient improved (EF >35%), SCD risk deemed to be negligible. These patients are expected to end WCD use and not receive an ICD.
- 2) Patient improved EF from start of WCD use (a positive change of at least 5 percentage points in EF), or has a borderline EF of 30-35%, but still has continued SCD risk (EF ≤ 35%). These patients are expected to continue to use the WCD for an additional 3 months.
- 3) Patient not improved from start of WCD use (no change or worsening of EF), EF<30% and has continued high SCD risk. Those on GDMT are expected to be evaluated for an ICD. Those not yet on GDMT may continue the WCD for an additional 90 days.

## 2.2 Secondary Objective(s)

The specific secondary objectives are to:

2.2.1 Observe the incidence and etiology of SCA and all sustained VT/VF arrhythmias during WCD use.

- 2.2.2 Observe the incidence of other arrhythmias during WCD use, such as asystole and supra-ventricular arrhythmias that are recorded by the device.
- 2.2.3 Collect ICD treatment data for those who receive an ICD, and evaluate for appropriateness.
- 2.2.4 Observe the effectiveness of the wearable defibrillator worn by this population in treating ventricular arrhythmias. Clinical outcomes data from any defibrillation or cardiac event will be collected, including device data on appropriate arrhythmia detection and shock delivery.
- 2.2.5 Evaluate the effect of wearable defibrillators on 90,180, 270, and 360-day mortality following WCD start in HF patients. Assessment of survival will be made at these time points for those entered into the study. A mortality review will be conducted to group all deaths as cardiac or non-cardiac, and sudden or non-sudden.
- 2.2.6 Collect economic and healthcare utilization data on all patients.

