## 3 Study Design

## 3.1 General Design

This study is designed as a multi-center prospective observational study of newly diagnosed HF with reduced EF patients to test the hypothesis that additional EF recovery occurs between 90 and 180 days as GDMT is achieved. Although the study doesn't start until day 90, all eligible, consenting patients will be entered into a registry at the start of WCD use. The pre-study registry will allow us to collect early (90 day) outcomes and data in those patients who are likely to be eligible for the study at day 90, or are eligible, but refuse the study at day 90.

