#### 8.1.1 Statistical design used for sample size calculation

This dataset will be used evaluate among all patients, if more than 5% of them will experience EF improvement between 90 and 180 days ( $n_5/n > 5\%$ ).

To calculate the number of samples (n), we first calculated  $n_4$ , then calculated n based on the following formula:

$$n = \frac{n_4}{P_{followup2}} * \frac{1}{p_{wcd}} * \frac{1}{P_{followup1}}$$

where  $p_{wcd}$  is the percentage of patients who will wear WCD beyond 90 days ( $n_1/(n_1+n_2+n_3)$ ,  $p_{followup1}$  and  $p_{followup2}$  are the percentage of patients with proper follow up from 0 to 90 days and from 90 days to 180 days respectively, both of the them equals to 0.85 (1-0.15=0.85).

To calculate sample size for  $n_4$ , we performed superiority test. The statistical hypothesis to be tested is:

[figure not shown]
$$H0: P \le P_0 + \delta \text{ vs } H1: P > P_0 + \delta$$

The sample size of superiority test is calculated as the following formula:

$$n_4 = p(1-p) \left( \frac{Z_{1-\alpha} + Z_{1-\beta}}{p - p_0 - \delta} \right)^2$$

where p is the actual proportion of patients who will have EF improvement ( $n_5/n_4$ ).  $p_0$  is the baseline proportion, and specified as 0.001 (close to 0).  $\delta$  is the test margin, since the hypothesis is that more than 5% of them will experience EF improvement between 90 and 180 days ( $n_5/n > 5\%$ ),  $\delta$  depends on  $p_{wcd}$  as  $\delta = 0.05/P_{wcd}$ . We also specify  $\alpha$  as 0.05,  $\beta$  as 0.1

As shown in figure above, sample size (n) depends both on p, the actual proportion of patients who will have EF improvement (p=n5/n4) and  $p_{wcd}$ , the percentage of patients who will wear WCD beyond 90 days ( $p_{wcd} = n_1/(n_1+n_2+n_3)$ ).In this study, we specify  $\alpha$  as 0.05,  $\beta$  as 0.1. We predict that about 1/3 patients will have continued WCD wear from 90 to 180 days; and actual proportion of WCD patients at 90 days to have further EF improvement is 23%. In this case, we plan to prescribe WCD to 868 patients (initial registry sample size), in order to have approximately 738 patients eligible for the study at day 90. If mid-study analysis shows continued WCD use to be far out of 1/3, then sample size will be re-adjusted as necessary.

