#### 8.3.6 Secondary Endpoint- Mortality

Descriptive statistics will be used to analyze the effect of wearable defibrillators on 180-day and 360 day mortality following discharge from HF. Kaplan-Meier curves and survival analysis will be performed both for aggregate mortality and independently for sudden and non-sudden cardiac deaths. Cause of mortality will be adjudicated by a committee independent of the sponsor. The influence of baseline characteristics and EF recovery status on mortality will be evaluated. Comparisons will be made using the Seattle Heart Failure model as a predictive tool of post-discharge mortality.

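### The plan aims to evaluate the effect of the WCD on mortality, but it has no group without a WCD and assesses survival only in patients who reached about day 90, so no such effect can be identified

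*Combined protocol and SAP*

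**What the plan says.** Section 2.2.5 is to "Evaluate the effect of wearable defibrillators on 90,180, 270, and 360-day mortality following WCD start in HF patients". It then fixes the population: "Assessment of survival will be made at these time points for those entered into the study". The neighbouring objectives 2.2.1, 2.2.2 and 2.2.4 are worded as observation; this one is not.

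Section 8.3.6 states: "Descriptive statistics will be used to analyze the effect of wearable defibrillators on 180-day and 360 day mortality following discharge from HF". It plans Kaplan-Meier curves for all deaths, and separately for sudden and non-sudden cardiac deaths. It adds: "Comparisons will be made using the Seattle Heart Failure model as a predictive tool of post-discharge mortality". No test, margin, calibration step or analysis by device status over time is given.

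The two sections differ in clock and time points. Section 2.2.5 uses four times from WCD start; section 8.3.6 uses two times from discharge.

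On design, sections 3.1.1 and 8.2 rule out randomization, the Study Summary lists no reference therapy, and section 4.1 requires a WCD prescription of everyone. Section 3.1 says the study does not "start until day 90, all eligible, consenting patients will be entered into a registry at the start of WCD use". Section 1.4.1 says "a prospective study is warranted to confirm that the WCD benefits these patients", naming both protection from sudden death and deferral of an ICD. Section 3.3, by contrast, presents the secondary endpoints, mortality included, as observational documentation.

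**The concern.** An effect needs a contrast: mortality with the device against mortality without it in comparable patients. The plan offers only a model prediction. A gap between observed and predicted mortality would also contain medication titration, EF recovery, ICD implantation and selection. The protocol's own background (section 1.3) links EF improvement to lower mortality, and absence of guideline therapy to higher one-year mortality.

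Selection is not a minor item here. Patients must live to about day 90 to enter, yet the comparison is with mortality predicted from discharge. That mismatch pushes the result in one direction, towards apparent benefit. The sponsor supplies the device and also acts as data coordination center and safety board (sections 11.3 and 11.5), so what the mortality result can and cannot show should be written down before it is analysed.

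**Working it through.** **1. Is there any contrast that isolates the WCD?**
- Concurrent group never prescribed a WCD: none (section 4.1).
- Random allocation: none (sections 3.1.1, 8.2).
- Comparison by device after day 90: the expected path follows EF, assessed sudden-death risk and medication status (section 2.1). For the improved group, "These patients are expected to end WCD use and not receive an ICD". Patients on and off the WCD therefore differ in prognosis (confounding by indication).
- External comparison: the Seattle model, which predicts overall risk and cannot separate the device from the other changes listed above.

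**2. Survivor selection.** Consent and entry take place at day 90 ± 14 (sections 4.1, 6.1.3), so 90-day mortality among entrants is close to zero by construction.

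Let q be the mortality before day 90 and S the survival to day 360 in the whole discharged population. If entrants are counted from day 0, their apparent 360-day mortality is 1 − S/(1 − q), against a true 1 − S. The shortfall is S × q/(1 − q). It cannot exceed q, because S is at most 1 − q.

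The documents give no q for this population. Section 1.1.1 cites over 10% at 90 days after discharge in one health system in 2006. I take 5% and 10% as illustrative assumptions, with S ranging from a constant hazard to no deaths after day 90:

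| q | S at constant hazard | Shortfall | Upper limit (no later deaths) |
|---|---|---|---|
| 5% | 0.95⁴ = 0.815 | 0.815 × 0.05/0.95 = 4.3 points | 5 points |
| 10% | 0.90⁴ = 0.656 | 0.656 × 0.10/0.90 = 7.3 points | 10 points |

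This shortfall arises with no device effect at all.

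**3. Planned WCD exposure (secondary).** The plan's own chain reproduces: 868 × 0.85 = 737.8, stated as 738 (section 8.1). One third of 738 is 246, inside the stated goal of 200-250 extended wearers.

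Let f be the share wearing from day 90 to 180. Section 8.1.1: "We predict that about 1/3 patients will have continued WCD wear from 90 to 180 days". The goal over the study cap (section 5.2) gives 200/600 or 250/600. Extended wear is 90 days (section 3.1.5).
- Days 90-360, share = f × 90/270: f = 1/3 or 200/600 gives 11.1%; 250/600 gives 13.9%.
- Days 0-360, share = (90 + f × 90)/360: 33.3% and 35.4%.
- Extended wear of 76 to 104 days: from (1/3) × 76/270 = 9.4% to (250/600) × 104/270 = 16.0% of days 90-360.
- f = 50% (assumption): 16.7% of days 90-360.

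**The case against.** The strongest reply is that the plan is already descriptive. The study is labelled observational, section 3.3 speaks of documenting events, and mortality has no test or success criterion. Section 2.1 reports outcomes for three day-90 groups. Section 8.3.6 separates sudden from non-sudden cardiac deaths and examines EF recovery status. This stands to the extent that a reader might infer that all deaths will simply be pooled and credited to the WCD, or that following the plan must produce a benefit claim. The documents support neither. But descriptive statistics do not estimate an effect, the three groups are EF and risk groups rather than device status at death, and 2.2.5 and 8.3.6 still state an effect.

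A reader might also infer that low wear time is what defeats the objective. That is too strong, for three reasons.
- On the objective's own clock, from WCD start, the share is 33-35%, not 11-14%.
- The one-third forecast is out of date. The sample size adjustment in section 8.1 says continued wear was higher than predicted, without a figure, and 13.9% divides a goal by a cap.
- Section 1.4.1 includes ICD deferral in the rationale. For a WCD-first strategy, deaths after wear ends would properly count.

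A third reply is that registry data cover the first 90 days. Section 2.2.5 limits the survival assessment to study entrants. Registry enrollment may itself come up to 30 days into wear (section 4.1), participation ends when WCD use ends (section 6.1.1), and adding registry time still supplies no comparator.

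**Conclusion.** The point holds as a mismatch between a stated causal aim and a single-cohort design. The missing comparator is decisive and depends on no number. Selection on survival to about day 90 makes the Seattle comparison misleading in a known direction. The illustrative size is 4.3 to 10 percentage points at 360 days, assuming 5% to 10% mortality before entry, entrants counted from day 0, and a prediction not conditioned on survival to entry. Section 8.3.6 does not mention such conditioning.

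The exposure figures are supporting context only. They ignore deaths, early exits and discretionary wear past day 180, which the Study Summary allows but does not quantify; zero exposure after day 180 should not be inferred. The 33-35% credits every entrant with 90 WCD days, although section 4.1.3 admits some who received an ICD earlier.

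This concerns a secondary objective. It does not touch the EF recovery endpoint, but it should be corrected before the mortality data are analysed.

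**What to change.** 1. In 2.2.5 and 8.3.6, replace the wording about an effect of the device with: *observed mortality in WCD-prescribed patients who survived to study entry at about day 90*. This also brings both into line with section 3.3.
2. Use one time origin and one set of time points in both sections.
3. In the Kaplan-Meier analysis, treat study entry as delayed entry, so that nobody is counted at risk before the day of entry.
4. Condition the Seattle prediction on survival to entry. Label it a benchmark of overall risk that supports no conclusion on WCD effect.
5. Tabulate sudden and non-sudden deaths, with patient-months, by device status at the time: WCD worn, WCD prescribed but not worn, ICD, no device. Label the table descriptive, since device status follows prognosis.

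Daily wear time is in the device records (section 7.1), and ICD implantation is recorded (sections 6.2.1.2 and 6.5). The documents do not show whether the CRF captures the implant date; that must be confirmed.

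The cost is a wording change, a short addition to the analysis text and one descriptive table. The sponsor gives up a causal mortality statement that the design cannot support.

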## 4 Study Subject

#### 4.1 Inclusion Criteria

The population for this study will be patients who had an ejection fraction (EF)  $\leq$  35% following hospitalization for newly diagnosed HF, and who have already been using a WCD for 90 days. Prior to 90 days, eligible patients will be enrolled into a registry. Registry patients will be enrolled during the first 30 days of WCD use.

All of the following must be true for enrollment into the registry (day 0 – 90 of WCD use):

- 4.1.1 Patients (≥18 years old) who were prescribed the WCD ≤ 10 days post-discharge after hospitalization for a primary reason of newly diagnosed HF with reduced EF (≤30 days since first HF hospitalization), with ischemic or nonischemic cardiomyopathy, and have used the WCD for no more than 30 days.
- 4.1.2 Patients who had an EF  $\leq$  35% during index hospitalization.

All of the following must be true for enrollment into the study (day  $90 \pm 14$ ):

- 4.1.3 Patients (≥18 years old) who were prescribed the WCD ≤ 10 days post-discharge after hospitalization for a primary reason of newly diagnosed HF with reduced EF (≤30 days since first HF hospitalization), with ischemic or nonischemic cardiomyopathy, and either 1) have already used a WCD for 90 ± 14 days or 2) were enrolled in the registry after 01-March-2019 and received an ICD prior to 90 days of WCD use.
- 4.1.4 Patients who had an EF  $\leq$  35% during index hospitalization. Of note, EF at 90  $\pm$  14 days post-hospitalization does not need to be low to be included in the study.

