#### 4.2 Exclusion Criteria

The exclusion criteria for enrollment into the registry (day 0-90) are: (none can be true)

- 4.2.1 Patients under 18 years old.
- 4.2.2 Patients who have an active unipolar pacemaker.
- 4.2.3 Patients with a physical or mental condition that could impair their ability to properly interact with the device.
- 4.2.4 Patients currently participating in an interventional clinical study.
- 4.2.5 Patients with any skin condition that would prevent wearing the device.
- 4.2.6 Patients with an advanced directive prohibiting resuscitation.

The exclusion criteria for enrollment into the study (day  $90 \pm 14$ ) are: (none can be true)

- 4.2.7 Patients under 18 years old.
- 4.2.8 Patients who have an active unipolar pacemaker.
- 4.2.9 Patients with a physical or mental condition that could impair their ability to properly interact with the device.
- 4.2.10 Patients currently participating in an interventional clinical study.

- 4.2.11 Patients with any skin condition that would prevent wearing the device.
- 4.2.12 Patients with an advanced directive prohibiting resuscitation.
- 4.2.13 Patients who have a QRS duration of ≥135 ms and are planned for cardiac resynchronization therapy during the study duration.
- 4.2.14 Patients with recent myocardial infarction or coronary revascularization (since start of WCD wear; i.e. 0-90 days of WCD wear).

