### 6.1.2 Subject recruitment into study

Once the site has determined that the patient meets the inclusion/exclusion criteria, the patient will be scheduled for their  $90 \pm 14\,$  day follow-up visit and echocardiogram, at which point they may be approached by the study staff for verification of inclusion/exclusion and for consent into the study.

- 6.1.3 Steps for screening and consent of patients:
  - 1) A chart review of patients prescribed the WCD (in the last 30 days) after hospitalization for HF will be used to evaluate patients for enrollment into the pre-study registry.
  - 2) Potentially eligible patients from the registry will be scheduled for a 90  $\pm$  14 day follow-up visit and echocardiogram.
  - 3) If eligible, at the 90  $\pm$  14 day follow-up visit, patients will be consented and enrolled into the study.

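### Mortality from WCD start is assessed only in patients alive to enter at about day 90, so the 90-day figure is near zero by design and the later figures are conditional on entry

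*Combined protocol and SAP*

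**What the plan says.** Section 2.2.5 sets a secondary objective on the effect of the WCD on mortality at 90, 180, 270 and 360 days, counted from WCD start. It then limits the population: "Assessment of survival will be made at these time points for those entered into the study".

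Entry comes late. Section 3.1 puts the start of the study at day 90. Section 6.1.3 says that at the day 90 ± 14 visit "patients will be consented and enrolled into the study". Section 4.1 adds a second route, for patients who "were enrolled in the registry after 01-March-2019 and received an ICD prior to 90 days of WCD use", but lists it under the same day 90 ± 14 enrolment. Section 4.2 excludes, at that point, "Patients with recent myocardial infarction or coronary revascularization" since WCD start, and some patients planned for resynchronisation therapy.

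Section 8.3.6 will "analyze the effect of wearable defibrillators on 180-day and 360 day mortality following discharge from HF". It adds that "Kaplan-Meier curves and survival analysis will be performed both for aggregate mortality", and that "Comparisons will be made using the Seattle Heart Failure model as a predictive tool of post-discharge mortality". It names no analysis population and no rule for late entry. Section 8.4 adds no method. Section 3.3 also speaks of mortality after discharge, while section 6.4 counts final survival from WCD start and asks sites for it in study patients only.

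**The concern.** The clock starts at WCD start or discharge, but the patients counted are those who lived to about day 90 and were then selected and consented. A conventional Kaplan-Meier curve that puts them at risk from day 0 credits each of them with 76 to 104 days in which death was impossible.

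Three things follow:
- The 90-day estimate carries almost no information.
- The 180-, 270- and 360-day estimates carry a label (mortality from WCD start, or from discharge) that does not describe them.
- If the Seattle model is scored at discharge, a prediction that includes early deaths is set against a cohort that cannot have them. Other things equal, that favours the sponsor's device, and both 2.2.5 and 8.3.6 speak of the device's effect on mortality.

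The sections also disagree with each other: two origins, and four time points against two. Under 4.1 the WCD may be prescribed up to 10 days after discharge, so the origins are not interchangeable.

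**Working it through.** The plan states no mortality estimate, so there is no figure to reproduce. The documents give no early mortality for this population. Section 1.1.1 cites over 10% at 90 days, but for heart failure patients in a veterans' health system. All rates below are therefore assumptions.

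**Inputs.** Entry window, days 76 to 104 (4.1, 6.2.3). Final assessment, day 360 ± 14 (6.2.7, 6.4). Assumed mortality over days 0 to 90: *d* = 1%, 3%, 5% or 10%. Assumed mortality over days 90 to 360 in survivors: *m* = 8%, constant hazard.

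**Apparent 90-day mortality in entrants.** Take entry as uniform over the window and the daily hazard as λ = −ln(1 − *d*)/90. Only entrants on days 76 to 89 can die by day 90. Average exposure before day 90 is 14²/(2 × 28) = 3.5 days, so the figure is about 3.5λ. For *d* = 3%, λ = 0.000338 and the result is 0.12%. If every patient entered on day 76, the figure would be 1 − exp(−14λ).

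| Assumed true 90-day mortality | 1% | 3% | 5% | 10% |
|---|---|---|---|---|
| Apparent, uniform entry | 0.04% | 0.12% | 0.20% | 0.41% |
| Apparent, all enter day 76 | 0.16% | 0.47% | 0.79% | 1.63% |

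**Survivorship part of the later figures.** True mortality at *t* is 1 − (1 − *d*)(1 − m_t). Survivors show m_t. The gap is *d*(1 − m_t), with m_180 = 1 − 0.92^(90/270) = 2.74%, m_270 = 1 − 0.92^(180/270) = 5.41% and m_360 = 8%.

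| Gap in percentage points | *d* = 1% | 3% | 5% | 10% |
|---|---|---|---|---|
| 180 days | 0.97 | 2.92 | 4.86 | 9.73 |
| 270 days | 0.95 | 2.84 | 4.73 | 9.46 |
| 360 days | 0.92 | 2.76 | 4.60 | 9.20 |

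With *m* = 4% the 360-day gaps are 0.96, 2.88, 4.80 and 9.60; with *m* = 12% they are 0.88, 2.64, 4.40 and 8.80. The formula treats entry as exactly day 90. A simulation with entry spread over the window gives 17.2 − 8.3 = 8.9 points rather than 9.2 in the 10% case.

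**Selection can offset this.** The 360-day gap closes when entrants' later mortality equals 1 − (1 − *d*)(0.92) = 8.92%, 10.76%, 12.60% or 17.20%, that is 1.12, 1.35, 1.58 or 2.15 times 8%. For *d* = 3%, true 360-day mortality is 10.76%. Entrant mortality of 6%, 8%, 10% or 12% then gives a gap of +4.76, +2.76, +0.76 or −1.24 points.

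**Length of follow-up from enrolment.** Shortest: entry on day 104, final assessment on day 346, 346 − 104 = 242 days. Longest: 374 − 76 = 298 days.

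**The case against.** **The study might include the registry.** The wording is loose. Section 8.1 counts WCD prescriptions for the study at 868, which 8.1.1 calls the registry sample size, and 8.3.4 counts arrests from the beginning of device use. But 3.1 says the study does not start until day 90, 6.1.1 ends registry participation on entry to the study, and 6.4.1 seeks final survival in study patients. The restriction in 2.2.5 is best read as excluding registry-only patients.

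**Early deaths are collected.** In part they are. Section 3.1 gives the registry the task of collecting early outcomes, 6.3 makes death a trigger for registry patients, and 12.1 lists a mortality questionnaire. A reader might infer that early deaths go unrecorded; the documents do not support that for deaths during WCD use. However, registry participation stops when WCD use ends, Table 1 has no survival row, and nothing brings registry deaths into 8.3.6.

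**The bias is not shown.** This largely stands. A reader might infer that the plan understates mortality by the gaps tabulated above. Those are the survivorship part only, under assumed rates. Entry also selects on continued WCD use or an early ICD, on the 4.2 exclusions and on a second consent. Patients who stop the WCD early after their ejection fraction improves do not meet the first entry route, and 1.3 cites a trial in which such improvement went with lower mortality. Entrants could therefore be at higher later risk than the patients left out.

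**Little depends on it.** The endpoint is secondary and descriptive, and no sample size rests on it. That limits the weight of the point but does not make the labels right.

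**Conclusion.** The point holds. As written, 2.2.5 asks for mortality from WCD start in a cohort that cannot contain deaths before day 76, and 8.3.6 does not repair this.

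The near-zero 90-day figure follows from the entry rule, whatever the true rate: about 0.04% to 0.4% for an assumed 1% to 10%. It is near zero rather than exactly zero, because a patient entering on days 76 to 89 can die by day 90. The later figures are mortality conditional on survival to, and selection into, entry. Survivorship alone lowers the 360-day figure by 0.9 to 9.2 points under assumed 1% to 10% early and 8% later mortality.

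The net difference from all WCD starters is not established in size or sign. Nor do the documents show that the Seattle comparison will favour the device: they do not say when the model is scored or how well it is calibrated in this population. The primary ejection fraction objective is unaffected. The wording should be corrected before analysis.

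**What to change.** 1. In 2.2.5, 3.3, 6.4 and 8.3.6, state one population, one time origin and one set of time points.
2. For study patients, drop the 90-day estimate. Choose one of three: keep WCD start as the time axis with delayed entry at the enrolment date; start the clock at enrolment; or landmark at day 104, when the entry window closes. Label results as mortality conditional on survival to, and entry into, the study.
3. Handle unequal follow-up by censoring. If time is counted from enrolment, say that time points beyond 242 days rest on partly censored follow-up.
4. State when the Seattle model is scored. Compare over the same window, with predictions conditional on survival to the same starting point (each patient's entry date or the landmark).
5. If day 0 to 90 mortality is reported, take it from the registry with delayed entry at registry consent (days 0 to 30). Label it mortality during WCD use, and note that censoring at WCD end may be informative.

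**Cost.** Wording in four sections and slightly more analysis work; the consent and WCD start dates should already be on file. The study cohort then yields no unconditional mortality estimate from WCD start. The day-360 number hardly changes: in simulation with no other selection it is 7.9%, 8.0%, 8.1% and 8.3% from WCD start for the four values of *d*, against 8.0%, 8.0%, 8.1% and 8.3% at 270 days from enrolment. What changes is the label, the time axis and the comparator.

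An unconditional estimate, if wanted, would need vital status for registry patients after WCD end. That means amending 6.1.1 and extra contacts for up to about 1400 − 600 = 800 patients at the caps in 5.2.
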